11.3 Planned Interim Analyses (if applicable)

No interim analysis is planned.

11.4 Final Analysis Plan

11.4.1 Analysis sets

Full Analysis set (FAS): All subjects who are randomized and receive at least one dose of study drug.

Evaluable subjects: Subjects in the FAS who have centrally confirmed AR+ status; these subjects are the subjects in the primary efficacy analysis.

Compound No.: GTx-024 Author: [name]

Per protocol set (PPS): All subjects with centrally confirmed AR+ who have baseline scans, receive at least 80% of the anticipated doses, and complete the week 24 RECIST 1.1 evaluation, and have no major protocol deviations.

Safety analysis set (SAS): All subjects who are randomized and receive at least one dose of study drug.

Safety analysis subjects will be analyzed in the treatment arm in which they are initially dosed. Efficacy analysis subjects will be analyzed according to the treatment arm to which they were randomized.

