7.3 Treatment Phase

The first dose of study drug will be administered on the day of randomization (Visit 2). GTx-024 will be administered daily for up to 24 months from randomization or until disease progression (whichever is sooner), subject's withdrawal of consent, or intolerability.

During the study treatment phase, the subjects will be scheduled for a visit every 6 weeks. Visit 7 at week 28 will only take place in subjects who have CR or PR at Visit 6 (week 24; see below).

The following tests and procedures will be performed during Visits 3, 4, 5, and 6 (weeks 6, 12, 18, and 24) in the treatment phase:

Review concomitant medications

Compound No.: GTx-024 Author: [name]

- Physical examination, including weight and vital signs (heart rate, respiratory rate, body temperature, blood pressure in a sitting position)
- ECOG performance status
- Blood sampling for: hematology, biochemistry, serum lipid profile, coagulation status, serum hormones, and PSA
- Urine analysis, if clinically indicated
- AE collection
- Subjects will be asked to complete a QoL questionnaire (EQ-5D-5L)
- GTx-024 drug accountability/dispensation

Radiologic assessments for anti-tumor effect will be done every 12 weeks whilst subjects receive treatment (Visits 4, 6, and thereafter). The same imaging technique must be used throughout the study in a given subject. Bone scans will be performed at screening and then every 12 weeks whilst subjects receive treatment (Visits 4, 6, and thereafter) in only those subjects with baseline bone metastases, or if clinically indicated. In addition, if any subject has CR or PR at Visit 6 (week 24), in compliance with RECIST 1.1 guidelines, a confirmation of the CR or PR (CT/MRI/bone scan) should be done 4 weeks later (Visit 7; week 28). The central imaging facility will also perform tumor volumetric assessment for the subjects undergoing CT scanning during Visits 4 and 6 (weeks 12 and 24). Blood sampling for CTC enumeration will be done at the same visits as the radiological assessments during the treatment phase; i.e., every 12 weeks whilst subjects receive treatment (Visits 4 and 6), but not at the confirmation of the CR or PR visit (Visit 7; week 28) or at Visits 8–13.

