7.4 End of Treatment (EOT) Visit

For all subjects the EOT visit should happen as soon as possible after the last dose of GTx-024 has been taken and no later than 3 days after that. The following tests and procedures will be performed during the EOT visit:

- Review of concomitant medications
- Physical examination, including weight and vital signs (heart rate, respiratory rate, body temperature, blood pressure in a sitting position)
- ECOG performance status
- Blood sampling for: hematology, biochemistry, serum lipid profile, coagulation status, and serum hormones
- Blood sampling for specific blood tests: PSA and CTCs (enumeration and gene expression)
- Urine analysis, if clinically indicated
- AE collection
- Radiological evaluation of the BC (as applicable CT/MRI/bone scan). Imaging results will be confirmed by a central imaging facility blinded to the GTx-024 dose.

Compound No.: GTx-024 Author: [name]

The same imaging technique must be used throughout the study in a given subject.

- Subjects will be asked to complete a QoL questionnaire (EQ-5D-5L)
- GTx-024 drug accountability
- Eye examination including best corrected distance visual acuity with refraction, intraocular pressure, slit lamp examination, and dilated fundus photography

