11.4.2 Definition of analysis endpoints; primary, secondary, tertiary, exploratory, safety

Primary efficacy endpoint

Tumor response in terms of clinical benefit will be assessed by RECIST 1.1 criteria from centrally read CT scans obtained at the 24 week assessment. Tumor response is judged relative to baseline tumor assessments. An evaluable subject will be considered to have a response of CB if the assessment indicates CR, PR, or SD. The primary assessment is among evaluable subjects in the FAS at 24 weeks in each of the 9 mg and 18 mg arms. An evaluable subject who does not have a week 24 assessment for any reason remains in the evaluable subset of the FAS and is considered a failure to achieve CB (CR, PR, or SD).

Secondary efficacy endpoints

CBR in the FAS and PPS at 24 weeks in each of the 9 mg and 18 mg arms

The following secondary efficacy endpoints will be assessed among subjects in each of the 9 mg and 18 mg arms among the evaluable subjects, the FAS, and the PPS:

ORR (CR or PR assessed by RECIST 1.1 criteria) at 24 weeks

Compound No.: GTx-024 Author: [name]

- Best (confirmed) overall response rate (BOR). BOR is defined as the best observed response for each subject up to and including the EOT. Reponses of CR or PR should be confirmed by a repeat assessment at least 4 weeks later.
- PFS: PFS is defined as the time from randomization until objective tumor progression or death due to any cause. Subjects who have no PFS events will be censored at the date of the last adequate tumor assessment. If the subject has no post-baseline tumor assessments, they will be censored at the time of randomization
- TTP: TTP is defined as the time from randomization until objective tumor
 progression or death due to disease progression. Subjects who have not
 progressed will be censored at the date of the last adequate tumor assessment. If
 the subject has no post-baseline tumor assessments but is known to be alive, they
 will be censored at the time of randomization
- Duration of response: Duration of response, in responders, is defined as the period from the date of initial CR or PR until the date of disease progression or death from any cause. Only subjects with BOR of CR or PR (i.e., responders) will be included in the analysis of duration of response. Subjects with no documented progression or death after CR or PR will be censored at the last date at which they are known to have had the CR or PR

Tertiary efficacy endpoints

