11.4.3.3 Second efficacy analysis

 The exact 95% confidence intervals about the CBR at week 24 among subjects in the FAS and PPS in each of the 9 mg and 18 mg arms will be constructed

The following secondary efficacy analyses will be performed in subjects in each of the 9 mg and 18 mg arms among the evaluable subjects, the FAS, and the PPS:

- The exact 95% confidence interval about the ORR (CR or PR) will be constructed at week 24
- The exact 95% confidence interval about the BOR will be constructed at week 24
- PFS: Median PFS and 95% confidence intervals will be estimated by the Kaplan-Meier method and the survival function and associated 95% confidence intervals will be constructed at key time points
- TTP: Median TTP and 95% confidence intervals will be estimated by the Kaplan-Meier method and the survival function and associated 95% confidence intervals will be constructed at key time points
- Duration of response: Median duration of response and 95% confidence intervals will be estimated by the Kaplan-Meier method and the survival function and

Compound No.: GTx-024 Author: [name]

associated 95% confidence intervals will be constructed at key time points for responders

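### The per-protocol set requires a completed week 24 RECIST evaluation, so deaths before it and week 12 progressors who follow the visit schedule drop out as if they were non-compliant

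*Combined protocol and SAP*

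**What the plan says.** Section 11.4.1 defines the PPS as centrally confirmed AR+ subjects "who have baseline scans, receive at least 80% of the anticipated doses, and complete the week 24 RECIST 1.1 evaluation", with no major deviations. Section 11.4.2 lists as a secondary endpoint "CBR in the FAS and PPS at 24 weeks in each of the 9 mg and 18 mg arms". It also places ORR, best overall response (BOR), PFS, TTP and duration of response in the PPS, alongside the evaluable subjects and the full analysis set (FAS). Section 11.4.3.3 plans exact 95% intervals "about the CBR at week 24 among subjects in the FAS and PPS in each of the 9 mg and 18 mg arms".

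The primary analysis treats the same situation differently. Section 11.4.2 states: "An evaluable subject who does not have a week 24 assessment for any reason remains in the evaluable subset of the FAS". Such a subject is scored as not achieving clinical benefit (CB), and Section 11.4.3.7 repeats this.

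The schedule decides who can have a week 24 evaluation:

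- Section 7.3, dosing: "GTx-024 will be administered daily for up to 24 months from randomization or until disease progression (whichever is sooner".
- Section 7.3, scans: "Radiologic assessments for anti-tumor effect will be done every 12 weeks whilst subjects receive treatment".
- Section 7.4: the end-of-treatment (EOT) visit, which includes imaging, takes place "after the last dose of GTx-024 has been taken and no later than 3 days after that".
- Section 7.5: the one-month follow-up lists no imaging.
- Sections 5.4.3 and 5.4.4 point the other way. Disease progression is a listed reason for withdrawal, and subjects who withdraw for any reason are asked to continue scheduled evaluations.

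**The concern.** A per-protocol set should remove subjects who did not follow the protocol. This one also removes subjects who followed it and failed early. Someone who progresses at week 12, stops drug as required and has her EOT scan has done everything the schedule asks, yet she has no week 24 evaluation. Someone who dies before week 24 cannot have one.

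Selection then depends on outcome. CBR and ORR are read at week 24, so the clause removes only subjects who could not be in either numerator. PFS and TTP run from randomization, but in the PPS they would be estimated largely in subjects selected for having reached week 24.

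At stake is how the secondary results read. An arm that fails the 9/44 rule could show a per-protocol CBR near the 30% target, with an interval that excludes 10%.

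**Working it through.** **The plan's own figure.** For the rule of at least 3/18 and then at least 9/44, the rejection probability is the sum over x from 3 to 18 of P(X1 = x) × P(X2 ≥ 9 − x), with X1 ~ Bin(18, p) and X2 ~ Bin(26, p). It is 0.0236 at p = 0.10 and 0.904 at p = 0.30. The stated one-sided 0.025 and 90% power reproduce. This rule is applied to the evaluable set, not the PPS.

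**Schedule.** The latest week 12 scan is on day 84 + 7 = 91. If the last dose is that day, the schedule's follow-up window ends on day 91 + 28 + 2 = 121. Using the general ±7 days of Section 7, it ends on day 126. The week 24 window opens on day 168 − 7 = 161, a gap of 40 or 35 days. An EOT scan could reach day 161 only if the last dose was on day 158 or later. A week 12 progressor who follows Sections 7.3 to 7.5 therefore has no week 24 evaluation.

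**Direction.** Let N be the evaluable subjects, x those with CB (or CR/PR) at week 24, and m those without a week 24 evaluation. None of the m is in x. The clause changes x/N to x/(N − m), which is at least x/N and equal only if m = 0 or x = 0.

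**Size in one arm.** The documents give no value for m, so it is assumed. Take 8/44 = 18.2%, which fails the rule and has 36 failures. Intervals are Clopper-Pearson.

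- A quarter (9) lack week 24: 8/35 = 22.9% (95% CI 10.4–40.1%).
- Half (18) lack week 24: 8/26 = 30.8% (14.3–51.8%).
- ORR with the same losses: 3/44 = 6.8% becomes 3/35 = 8.6% or 3/26 = 11.5%.

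**Expected size.** Assume a constant hazard and loss only through week 12 progression. Let p be the true week 24 rate, S12 = √p the share event-free at week 12, and r the assumed share of week 12 progressors still evaluated at week 24 and counted as failures. The share in the PPS is d = S12 + r(1 − S12). PPS CBR and PPS week 24 PFS are both p/d. S12 is 0.316 for p = 0.10 and 0.548 for p = 0.30.

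| r | d (p = 0.10) | true 10% reads | d (p = 0.30) | true 30% reads |
|---|---|---|---|---|
| 0% | 0.316 | 31.6% | 0.548 | 54.8% |
| 50% | 0.658 | 15.2% | 0.774 | 38.8% |
| 80% | 0.863 | 11.6% | 0.910 | 33.0% |
| 100% | 1.000 | 10.0% | 1.000 | 30.0% |

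Week 12 PFS in the PPS is S12/d. For p = 0.30 the true 54.8% reads 100%, 70.8%, 60.2% and 54.8% in the same order.

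**Dose criterion.** Section 11.4.1 gives no period for anticipated doses. If it were 168 days, 80% is 134.4 days. Stopping on day 77 to 91 gives 77/168 = 46% to 91/168 = 54%, so the same subjects would be removed even if the week 24 clause were repaired.

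**Check of the repair.** Suppose early progressors and deaths are admitted, and a share q of those event-free at week 12 drop out before week 24 (assumed 10% to 30%). Amended PPS CBR is p(1 − q)/[(1 − S12) + S12(1 − q)]. For p = 0.30 this is 0.270/0.945 = 28.6% at q = 0.1 and 0.210/0.836 = 25.1% at q = 0.3, against primary CBRs p(1 − q) of 27.0% and 21.0%. Week 24 PFS in that set also reads 28.6% to 25.1%, below the true 30%, so PFS and TTP need separate treatment.

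**The case against.** The strongest objection is that a reader might infer that most week 12 progressors leave the PPS, and the documents do not settle this. Sections 5.4.3 and 5.4.4 together ask subjects withdrawn for progression to continue scheduled evaluations. Section 8.1 bases treatment decisions on the Investigator's assessment, so a subject with progression on central review only may stay on drug to week 24. Sections 7.3 to 7.5 point the other way. The share retained is unknown, and at 80% retention the shift is small. This objection stands. Exclusion is certain only for deaths and for progressors who follow the treatment-linked schedule.

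A reader might also infer that the actual PPS CBR must exceed the primary CBR. That does not follow. The dose and major-deviation criteria can remove subjects with CB: if two of the 18 removed above had CB, the rate is 6/26 = 23.1%, not 30.8%. Nor does the argument extend to BOR, since "BOR is defined as the best observed response for each subject up to and including the EOT" lets an early responder without a week 24 evaluation count. With 18 of 44 removed, 4/44 = 9.1% becomes 3/26 = 11.5% if one responder is lost but 2/26 = 7.7% if two are.

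Finally, the PPS appears in no objective or outcome measure (Sections 3.1, 3.2.2) and carries no decision rule, and the conservative primary estimate will be reported beside it. That limits severity but does not make the definition sound. Section 11 refers further detail to a separate SAP that is not in the supplied text. Section 11.4.1, however, states the PPS definition in full and does not defer it.

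**Conclusion.** The point holds as a defect in a supportive analysis set, of minor to moderate severity. The direction of the week 24 clause taken alone is certain for CBR and ORR, and so is the exclusion of every death before that evaluation. The size is not known. It runs from no shift with full retention of week 12 progressors to an apparent 31.6% for a true 10%, or 54.8% for a true 30%, with none retained. Those figures rest on the constant hazard, on loss only through week 12 progression, and on an assumed retention share.

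A failing arm whose PPS rate sits near 30% might be read as a threat to the go/no-go decision. The documents do not support that: the primary CBR, the evaluable-set and FAS analyses, and the 3/18 and 9/44 rules (Sections 11.2, 11.4.3.2) do not use the PPS.

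**What to change.** 1. In Section 11.4.1, admit to the PPS a subject who either has the week 24 RECIST evaluation or lacks it because of earlier death or disease progression; count the latter as no CB. Where a week 24 evaluation exists, let its central read govern, exactly as in the primary analysis. Otherwise a subject with progression on central review only at week 12 could be CB in the primary analysis and a failure in the PPS.
2. Count anticipated doses only up to the first of end of treatment for progression, death, or the week 24 visit, so that the 80% criterion does not remove the same subjects.
3. In Sections 11.4.2 and 11.4.3.3, report PFS and TTP in the evaluable subjects and the FAS only, as Sections 3.1 and 3.2.2 already specify, or in the PPS only from a week 24 landmark.

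The cost is a few sentences in these sections and the SAP, using data already collected. PPS CBR and ORR will be less favourable and closer to the primary result, and the PPS PFS and TTP outputs are dropped or landmarked.

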11.4.2 Definition of analysis endpoints; primary, secondary, tertiary, exploratory, safety

Primary efficacy endpoint

Tumor response in terms of clinical benefit will be assessed by RECIST 1.1 criteria from centrally read CT scans obtained at the 24 week assessment. Tumor response is judged relative to baseline tumor assessments. An evaluable subject will be considered to have a response of CB if the assessment indicates CR, PR, or SD. The primary assessment is among evaluable subjects in the FAS at 24 weeks in each of the 9 mg and 18 mg arms. An evaluable subject who does not have a week 24 assessment for any reason remains in the evaluable subset of the FAS and is considered a failure to achieve CB (CR, PR, or SD).

Secondary efficacy endpoints

CBR in the FAS and PPS at 24 weeks in each of the 9 mg and 18 mg arms

The following secondary efficacy endpoints will be assessed among subjects in each of the 9 mg and 18 mg arms among the evaluable subjects, the FAS, and the PPS:

ORR (CR or PR assessed by RECIST 1.1 criteria) at 24 weeks

Compound No.: GTx-024 Author: [name]

- Best (confirmed) overall response rate (BOR). BOR is defined as the best observed response for each subject up to and including the EOT. Reponses of CR or PR should be confirmed by a repeat assessment at least 4 weeks later.
- PFS: PFS is defined as the time from randomization until objective tumor progression or death due to any cause. Subjects who have no PFS events will be censored at the date of the last adequate tumor assessment. If the subject has no post-baseline tumor assessments, they will be censored at the time of randomization
- TTP: TTP is defined as the time from randomization until objective tumor
 progression or death due to disease progression. Subjects who have not
 progressed will be censored at the date of the last adequate tumor assessment. If
 the subject has no post-baseline tumor assessments but is known to be alive, they
 will be censored at the time of randomization
- Duration of response: Duration of response, in responders, is defined as the period from the date of initial CR or PR until the date of disease progression or death from any cause. Only subjects with BOR of CR or PR (i.e., responders) will be included in the analysis of duration of response. Subjects with no documented progression or death after CR or PR will be censored at the last date at which they are known to have had the CR or PR

Tertiary efficacy endpoints

The following tertiary efficacy endpoints will be assessed among subjects in each of the 9 mg and 18 mg arms among the evaluable set of subjects and among the FAS:

- PSA: PSA will be obtained during routine laboratory assessments and results at each scheduled assessment will be compared with baseline along with percentage change from baseline
- QoL: QoL will be obtained using the EQ-5D-5L, with each scheduled assessment compared with baseline
- CTCs: The number of CTCs will be obtained at each scheduled assessment and compared with baseline

Compound No.: GTx-024 Author: [name]

- Duration of prior CB: The impact of duration of prior CB on outcome (CB response at week 24, PFS, TTP, duration of response)
- Time from diagnosis of metastases to randomization: The impact of time from diagnosis of metastases to randomization on outcome (CB response at week 24, PFS, TTP, duration of response)
- Tumor volume and change from baseline in tumor volume
- Pharmacokinetics: GTx-024 and GTx-024 glucuronide plasma concentrations and outcome (CBR at weeks 16 and/or 24)

Safety endpoints

The following safety endpoints will be assessed among evaluable subjects as well as all subjects enrolled and treated:

- AEs and concomitant medications
- Laboratory examinations (clinical chemistry, hematology, and urinalysis)
- Physical examinations
- Vital signs
- ECOG performance status
- Eye examinations

Pharmacokinetic endpoints

 Plasma concentrations of GTx-024 18 mg and GTx-024 glucuronide at each assessment

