3.2 Study Outcome Measures

3.2.1 Primary Efficacy Outcome Measures

Response of CB at 24 weeks, in a subject with centrally confirmed AR+ status.

CB is defined as a CR, a PR, or SD as measured by RECIST 1.1 and confirmed by a central image-reading facility blinded to the GTx-024 dose received.

For subjects with non-measurable (non-target) disease only at baseline, SD is defined as those with non-CR/non-progressive disease (PD) combined response.

Compound No.: GTx-024 Author: [name]

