4 STUDY DESIGN

This is an open label, multicenter, multinational, randomized, parallel design Phase 2 study to assess the efficacy and safety of GTx-024 in postmenopausal subjects with ER+/AR+ BC. Subjects will be randomized to receive either GTx-024 9 mg or 18 mg given PO daily for up to 24 months. Each dose arm will be treated independently and each assessed for efficacy using Simon's two-stage (optimal) design¹. Subjects will be randomized in a 1:1 fashion to one of the two dose arms. Randomization will be stratified by subjects presenting with bone only metastases and all other subjects, and further by setting of immediately preceding therapy (adjuvant setting or metastatic setting) in order to balance the proportion of subjects with these presenting features in each dose arm. There is no intent to statistically compare the two dose arms, but to determine whether either or both doses result in an acceptable CBR, defined as the proportion of evaluable subjects (i.e., subjects with centrally confirmed AR+ and who receive at least one dose of study drug) with either CR, PR, or SD by RECIST 1.1 at week 24, consistent with 30% while maintaining an acceptable safety profile. Given such a result, future exploration of GTx-024 in ER+/AR+ BC would be warranted at that dose level.

Thirty-six to 88 (36–88) subjects with centrally confirmed AR+ who receive at least one dose of study drug (evaluable subjects) will be needed for primary efficacy analysis purposes and will be a subset of the FAS. Thirty-six to one hundred and eighteen (36–118) subjects, including replacement subjects, will be randomized in a 1:1 fashion to receive a daily PO dose of either GTx-024 9 mg or 18 mg. Thirty of the aforementioned subjects may be considered replacement subjects to account for lack of centrally confirmed AR+ status or for the rare subject who is randomized but does not receive study drug (assumes 25% of enrolled subjects are not evaluable for the primary efficacy analysis). Other statistical parameters that are part of the sample size calculation are α = 0.025 (one-sided) and power = 90%. The first stage in each study arm will be assessed among the first 18 evaluable subjects. If at least 3/18 subjects achieve CB (defined as CR, PR, or SD) at week 24, the arm will proceed to the second stage of recruitment up to a total of 44 evaluable subjects per arm. Otherwise, the arm will be discontinued for lack of efficacy. Statistical significance, i.e., rejection of

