- 7. Subject must have either measurable disease or bone-only non-measurable disease, evaluable according to RECIST 1.1
- 8. Adequate organ function as shown by:
 - Absolute neutrophil count (ANC) ≥ 1,500 cells/mm³
 - Platelet count ≥ 100,000 cells/mm³
 - Hemoglobin (Hgb) ≥ 9.0 g/dL
 - Serum aspartate aminotransferase (AST) and alanine transaminase (ALT) ≤ 2.5 upper limit of the normal range (ULN) (or ≤ 5 if hepatic metastases are present)
 - Total serum bilirubin ≤ 2.0 × ULN (unless the subject has documented Gilbert Syndrome)
 - Alkaline phosphatase levels ≤ 2.5 × ULN (≤ 5 × ULN in subjects with liver metastasis)
 - Serum creatinine ≤ 2.0 mg/dL or 177 µmol/L
 - International normalized ratio (INR) or activated partial thromboplastin (aPTT)
 1.5 × ULN (unless on anticoagulant treatment at screening)
- Subject has an Eastern Cooperative Oncology Group (ECOG) performance status⁴
 o or 1
- 10. Subject is able to swallow capsules
- 11. Able and willing to give voluntary, written and signed informed consent before any screening procedure and according to local guidelines

Compound No.: GTx-024 Author: [name]

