5.4.2 Masking Procedures

Treatment periods will be open label.

Tumor lesions will be assessed using RECIST 1.1 at the site based on the local reading facility; however, scans will also be sent to the central imaging facility, blinded to the GTx-024 dose, for final efficacy outcomes analysis.

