7.1 Screening

Screening assessments must occur within 28 days prior to randomization for determination of subject's overall eligibility. Informed consent will be obtained from the subjects before any other study procedure or test. AEs will be collected from the signing of the informed consent form (ICF). The following tests and procedures will be performed during the screening visit (Visit 1):

- Eligibility criteria check
- Subject medical history (current and past)
- Demography (age, gender, race)
- Diagnosis and extent of cancer
- Review of prior/concomitant medications, including previous and current anticancer treatment
- Physical examination, including height, weight, and vital signs (heart rate, respiratory rate, body temperature, blood pressure in a sitting position)
- ECOG performance status
- ECG

Compound No.: GTx-024 Author: [name]

- Blood sampling for: screening for HIV, HBV, and HCV
- Blood sampling for: hematology, biochemistry, coagulation status, and serum pregnancy test
- Blood sampling for specific blood tests: PSA
- Urine analysis
- AE collection (from the moment of ICF signing)
- Radiological evaluation of the BC (as applicable CT/MRI/bone scan). Imaging
 results will be confirmed by a central imaging facility blinded to the dose of
 GTx-024 to be received, although a subject will be enrolled based on the local
 imaging and Investigator's assessment. The central imaging facility will also
 perform tumor volumetric assessment for the subjects undergoing CT scanning. It
 is recommended these procedures are done as close to the randomization visit
 (Visit 2) as possible (if possible within 7 days prior to randomization)
- Review of medical history to confirm the hormonal receptor status of the tumor (ER, HER2). ER status will be confirmed by a local laboratory if not available in the subject's medical history. AR status will be confirmed at a central laboratory
- Eye examination including best corrected distance visual acuity with refraction, intraocular pressure, slit lamp examination, and dilated fundus photography (must be completed between Day –28 and Day –1)

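### Section 11.4.2 takes the primary clinical benefit call from CT scans alone, which conflicts with Section 3.2.1 and with the week 24 bone scans and MRI that the protocol plans or permits

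*Combined protocol and SAP*

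**What the plan says.** Section 11.4.2, under the primary efficacy endpoint, states that CB is "assessed by RECIST 1.1 criteria from centrally read CT scans obtained at the 24 week assessment". CT is the only modality named, and nothing is said there about subjects without measurable disease.

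Other parts of the protocol are wider:

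- **Section 3.2.1** requires the RECIST 1.1 result to be "confirmed by a central image-reading facility blinded to the GTx-024 dose received", with no limit on modality. For non-measurable disease only, "SD is defined as those with non-CR/non-progressive disease (PD) combined response".
- **Section 5.1, criterion 7:** "Subject must have either measurable disease or bone-only non-measurable disease, evaluable according to RECIST 1.1". Criterion 6 lists the bone scan among the sources of evidence for recurrence or progression.
- **Section 4:** "Randomization will be stratified by subjects presenting with bone only metastases and all other subjects".
- **Sections 7.3 and 8.1** schedule bone scans at screening and every 12 weeks, so including Visit 6 (week 24), "in only those subjects with baseline bone metastases, or if clinically indicated". Section 8.1 gives their purpose as assessing bone metastases. It also allows MRI of the abdomen when contrast is contraindicated.
- **Section 5.4.2:** "scans will also be sent to the central imaging facility, blinded to the GTx-024 dose, for final efficacy outcomes analysis". Section 8.1 repeats this.
- **Sections 7.1 and 7.4** list CT, MRI and bone scan together at screening and end of treatment, with central confirmation.

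**The concern.** Section 11.4.2 is where a central reader or programmer would look for the definition of the primary endpoint. Someone who follows it as written would use the week 24 CT and set the bone scan aside. A subject with stable CT and progression seen only on the week 24 bone scan would then count as having CB. The rule that treats a missing assessment as failure would not correct this, because she has a week 24 assessment. Local reading would not correct it either: it governs treatment decisions (Section 8.1), while the endpoint uses the central read.

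The error runs one way, from no benefit to benefit. Each arm is judged on small counts, at least 3 of 18 and then at least 9 of 44, so one or two subjects can change the decision for an arm.

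**Working it through.** **1. The passages side by side**

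| Question | Section 11.4.2 | Elsewhere |
|---|---|---|
| Which images feed the week 24 CB call? | CT | Not limited (3.2.1); scans in general go to the central facility (5.4.2, 8.1) |
| What counts as SD in non-measurable disease only? | Not stated | Neither CR nor PD on combined response (3.2.1) |
| Can bone-only disease enter? | Not addressed | Yes, and it is a stratum (5.1, 4) |
| Are bone scans done at week 24? | Not mentioned | Yes, with baseline bone metastases or if clinically indicated (7.3, 8.1) |
| Is MRI possible? | Not mentioned | Yes, for the abdomen (8.1) |

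Section 11.4.2 therefore names a source that excludes modalities used elsewhere at the same time point. This is a conflict between sections, not merely missing detail.

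The schedule footnotes do not settle it. Footnote 7, which names the blinded central reader, opens with CT and MRI. Footnote 9, on bone scans, gives only their frequency and the subjects concerned.

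**2. Who could be affected**

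Treatment continues until progression (7.3), and the local reading determines PD (8.1). Bone progression found at week 12 would normally have ended treatment already. Chest, abdomen and pelvis CT shows part of the skeleton. What remains is mainly progression first seen at week 24 and only on the bone scan. The protocol gives no rate for this.

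**3. The decision rule that the CB call feeds**

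Inputs from Sections 11.1 and 11.2: null rate 0.10, alternative 0.30, one-sided alpha 0.025, power 90%, at least 3/18 and then at least 9/44. The second stage adds 44 − 18 = 26 subjects. With true or apparent rate p,

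P(pass) = Σ over x = 3 to 18 of Bin(x; 18, p) × P(Bin(26, p) ≥ 9 − x).

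- p = 0.10: 0.0236, within the stated 0.025.
- p = 0.30: 0.904, which meets the stated 90%.

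The plan's design figures are reproduced.

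**4. Sensitivity to misread subjects (illustration only)**

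Let f be the assumed share of subjects truly without CB who are read as having it. At a true rate of 0.10 the apparent rate is p = 0.10 + 0.90f, and the mean number misread per 44 is 44 × (p − 0.10).

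| Apparent rate p | f = (p − 0.10)/0.90 | Mean misread per 44 | P(pass) |
|---|---|---|---|
| 0.10 | 0 | 0 | 0.0236 |
| 0.11 | 1.1% | 0.44 | 0.0403 |
| 0.12 | 2.2% | 0.88 | 0.0636 |

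The values of f are assumptions. The table would be the same for misclassification from any cause, so it shows how sensitive the rule is and says nothing about how often bone-scan findings would be missed.

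**The case against.** The strongest reply is that the protocol, read as a whole, already resolves the wording. The sentence itself invokes RECIST 1.1. Section 3.2.1 uses a combined response and sets no CT limit. Section 11.2 defines CB by central review without naming a modality. Section 4 speaks of the week 24 RECIST 1.1 assessment. Sections 5.4.2 and 8.1 send scans to the central facility for the efficacy analysis, and Sections 7.3 and 8.1 name the bone scan for confirming a week 24 CR or PR. This stands as to intent: one combined central read is the probable meaning. It does not remove the conflict, because Section 11.4.2 makes a positive statement that says something else.

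Section 11 also calls itself an overview and defers detail to a separate SAP, whose text is not in the document reviewed. That SAP might settle the point. But imaging modality is not among the topics that Section 11 says it will cover.

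A further reply is that the documents do not reproduce the RECIST 1.1 rule for bone scans, so a change seen only on a scan may not always be PD. This is fair as a limit. The protocol does treat the bone scan as evidence of progression in inclusion criterion 6, which is enough to give the direction of the bias but not its size.

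Three stronger readings are tempting, and the documents do not support them:

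- *Bone scans will be ignored.* The other sections point the other way.
- *The type I error is 4% to 6%.* Those figures rest wholly on assumed misread rates, and the true number of affected subjects could be zero.
- *Bone-only subjects will be scored as not assessed.* Section 8.1 plans CT without exempting them, and the failure rule turns on a missing assessment, not a missing CT.

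**Conclusion.** The point holds as an internal contradiction in the operative definition of the primary endpoint. Section 11.4.2 restricts the call to CT and drops the rule for non-measurable disease, against Section 3.2.1, the eligibility and stratification of bone-only disease, and the week 24 imaging plan. Followed literally, it would exclude progression seen only on the week 24 bone scan and push the clinical benefit rate upward. That direction assumes that such a finding counts as progression.

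The size cannot be estimated from the documents. The affected group is probably small, but on cut-offs of 3/18 and 9/44 one or two misclassified subjects could decide an arm. The wording should be settled before central reading starts, since a choice made later in an open-label trial could look driven by the data.

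**What to change.** In Section 11.4.2, replace "assessed by RECIST 1.1 criteria from centrally read CT scans obtained at the 24 week assessment" with:

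> assessed as the blinded central RECIST 1.1 overall response at the 24 week assessment, based on all protocol imaging at that assessment (CT, MRI and bone scan as applicable), with SD for subjects with non-measurable disease only defined as in Section 3.2.1

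Optionally, add to footnote 9 in both copies of the Schedule of Events that bone scans are part of the blinded central read. This only makes explicit what Sections 5.4.2 and 8.1 already provide. If the separate SAP restates the endpoint, it should use the same wording.

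The cost is one sentence and, if wanted, one footnote in two places. The bone scans are already scheduled, and scans already go to the central facility. N = 44 per arm, 3/18 and 9/44 are unchanged.
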